Study Design

A clustered, multiple-baseline design will be used to examine the impact of implementation support on clinicians' fidelity, use and ratings of MBC appropriateness, acceptability and fidelity. Approximately 50 SMH clinicians will participate from up to three school districts as a part of their regular professional development activities. In these school districts, measurement based care implementation is a district-wide quality improvement initiative. All clinicians will receive the same implementation supports; there is no random assignment to condition. Following an initial control period of at least 1 month, school districts will start receiving implementation supports. Baseline MBC use, attitudes, acceptability, feasibility and appropriateness (per clinician self-report) will be collected, as well as needs assessment data from clinician surveys to inform necessary adjustments to the implementation supports. Baseline engagement and student outcomes will be collected after initial clinician training session. MBC implementation outcomes (i.e., MBC use, attitudes, acceptability, appropriateness, and feasibility), engagement and student outcomes will be collected at 3-month and 6-month follow-up during intervention supports, plus a 9-month follow-up interval. This allows clinicians in the school districts to be compared to each other and to their own baseline. The primary comparison is pre-post ratings of implementation outcomes for all N=50 clinicians. The secondary comparisons are pre-post ratings of engagement and student outcomes, and between-agency differences.

Clinicians will receive a 3-hour professional development on MBC in Fall 2022 that is required by the three participating school districts. Monthly, post-training group consultation calls will be conducted for 6-months, and online, self-report surveys will be collected at baseline, 3-month, 6-month and 9-month intervals. Clinicians will be asked to implement measurement-based care, using the Better Outcomes Now (BON) online feedback system, with at least 5 students each. Data in BON are deidentified and this activity is part of routine care provided by clinicians, so does not require special consent. These data will also be used to inform group consultation supporting clinicians' practices.

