Approximately 150 parents of students working with the participating clinicians will be recruited and enrolled using active consent. Parents will be asked to consent to 1) permission to review student records for goals and progress; and 2) 25-minute study phone calls at baseline, 3-months, 6-months and 9-months to provide parent-reported information on engagement and child outcomes throughout treatment. These data will be used to assess family engagement and child outcomes associated with measurement-based care delivered by the clinicians.

This study will be conducted in established, commonly accepted educational settings where mental health services are routinely provided. The interactions between children, families, their SMH clinicians on school campuses are part of their regular service delivery. The MBC training clinicians provide will be integrated into services as usual. The MBC measures and practices are considered best practices, and evidence-based practices, for children's mental health services. However, clinicians in usual care settings including schools under-implement MBC. They do not pose any risk when integrated into usual care. There are no group assignments. Clinician and parent reported study

measures are retrospective throughout the school year that SMH services are being provided.

Study Date Range and Duration

This study is expected to last approximately two calendar years, with each cohort of clinicians and parents recruited within the 2021-2022 or 2022-23 school year as the participating sites are school districts. Parents will be recruited in fall of 2021, and then again in the fall of 2022, based on clinicians who are signed up to receive the district-required MBC training each fall. Data collection will occur at baseline, 3 months, 6 months and 9 months.

Number of Study Sites (2)

[REDACTED] Public Schools, [ADDRESS REDACTED]

[REDACTED] Public Schools, [ADDRESS REDACTED]

*Other school district sites may be identified depending on their interest in participation.

Primary Outcome Variables

The primary objective of this study is to examine implementation outcomes.

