Implementation outcomes are selected from a published taxonomy of outcomes include acceptability, appropriateness, feasibility and fidelity. **Acceptability, appropriateness, and feasibility** will be measured by clinician self-report on the Acceptability of Intervention Measure (AIM), Intervention Appropriateness Measure (IAM), and Feasibility of Intervention Measure (FIM) via web-based, clinician-report survey. These 4-item measures were developed based on input from 36 implementation scientists and 27 mental health professionals; structural validity, test-retest reliability, and sensitivity to change have been established. **MBC use (fidelity)** will be evaluated by chart review in BON for evidence of two progress monitoring measures, the Session Rating Scale 3.0 (SRS) and Outcomes Rating Scale 3.0 (ORS). The MBC training provided as part of this study will include how to use MBC and document it in BON. The ORS will be completed before each session to assess prior-week functioning, and the SRS will be completed at the end of the session to assess student/parent perceptions of alliance with the clinician.

Secondary and Exploratory Outcome Variables

The secondary objective of this study is to examine effectiveness outcomes.

Effectiveness outcomes of MBC will be measured using actual scores on the SRS and ORS, as documented in the student's service record. The SRS and ORS are part of the Partners for Change Outcome Management System (PCOMS), a system used to enhance patient involvement in mental health services and improve therapeutic alliance and treatment progress. **Student engagement** will be measured by the SRS. **Parent engagement** will be measured by the Therapeutic Alliance Scales for Caregivers and Parents. **Symptoms and functioning** will be measured using the ORS. Emotional and behavioral symptoms will also be measured by the Pediatric Symptom Checklist, 35-item version (PSC-35) which has well-established reliability and validity to assess and monitor progress of internalizing and externalizing symptoms for children ages 4-18. The Therapeutic Alliance Scales for Caregivers and Parents and the PSC-35 will be collected directly from parents/guardians over the phone at baseline and follow-up intervals.

Study Population

This study plans to enroll up to 150 parents/legal guardians of children or adolescents receiving SMH treatment from one of the 50 participating clinicians. We anticipate SMH

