3.1 Hypothesis

Hypothesis 1: Clinicians' ratings of MBC implementation outcomes will increase following implementation strategies provided as compared to ratings during the baseline period. (Primary Objective)

Hypothesis 2: MBC fidelity (per MBC feedback system review) and use (per clinician self-report) will increase following implementation strategies provided as compared to ratings during the baseline period, with documentation of measure collection more prevalent than documentation of discussing progress or changing the treatment plan in accordance with measures. (Primary Objective)

Hypothesis 3: MBC fidelity and use will be positively associated with engagement and mental health symptom and functioning progress over time. (Secondary Objective)

Although underpowered to establish outcomes as a result of strategies applied with certainty, this pilot will provide mentored research experience and preliminary data for planning a future large-scale hybrid trial.

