4.1.1 General Design Description

A clustered, multiple-baseline design will be used to examine the impact of the implementation support condition on clinicians' fidelity, use and ratings of MBC appropriateness, acceptability and fidelity. Approximately 50 SMH clinicians will be recruited to participate from two school districts. All clinicians will receive the same implementation supports; there is no random assignment to condition. Following an initial control period of at least 1 month, school districts will start receiving implementation supports. During the initial control period, baseline MBC use, attitudes, acceptability, feasibility and appropriateness (per clinician self-report) will be collected, as well as needs assessment data from clinician surveys to inform necessary adjustments to the implementation supports. Baseline engagement and student outcomes will be collected after initial clinician training session. MBC implementation outcomes (i.e., MBC use, attitudes, acceptability, appropriateness, and feasibility), engagement and student outcomes will be collected at 3-month and 6-month follow-up during intervention supports, plus a 9-month follow-up interval. This allows clinicians in the two school districts to be compared to each other and to their own baseline. The primary comparison is pre-post ratings of implementation outcomes for all N=50 clinicians. The secondary comparisons are pre-post ratings of engagement and student outcomes, and between-agency differences.

Study Date Range and Duration

This study is expected to last approximately one calendar year from recruitment to follow-up, aligned with the 2021-2022 and 2022-23 academic years as the participating sites are school districts. Clinicians will start training and consultation in the fall of 2021 or 2022 and parents/guardians will be recruited in the fall of 2021 or 2022. Data collection will occur at baseline, 3 months, 6 months and 9 months.

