5.3 Statistical Method

5.3.1 Statistical Design

Quantitative Analyses

Quality control checks of the data and examination of variable distributions will be performed prior to formal analysis. There are *three* types of outcomes: (1) clinician report of acceptability, appropriateness, and feasibility (implementation outcomes), (2) clinician use of MBC (also an implementation outcome, fidelity), and (3) student engagement, progress and outcomes (effectiveness of MBC). For (1) and (2), the primary analysis will be a multilevel growth model with time (Level 1) nested within clinician (Level 2) for each of the implementation outcomes as they are clinician self-reported on clinician surveys. We will examine linear change of time as a continuous measure as well as time by time transitions across the longitudinal intervals of data collection. Attitudes toward MBC and other

independent variables (e.g., clinician professional and demographic characteristics, consultation call attendance, school district) will be entered into the models to examine correlations. In particular, we hypothesize parallel growth between attitudes and use of MBC over time.

For (3) we will conduct a 3-Level multilevel growth model with time (Level 1) nested within student/parent reported outcome (Level 1) nested within clinician (Level 3). Models will be estimated for each parent-reported outcome (e.g., parent-reported engagement, parent-reported symptoms on the PSC-35). Independent variables that will be entered as covariates in these models include MBC implementation outcomes, with the specific hypothesis that MBC use will be predictive of positive engagement and symptom reduction.

Also, for (3), the ORS and SRS are assessed at each session, hence, a mixed effects regression model will be used that accounts for intra-student correlation across student sessions and clustering of students within clinician. The unit of analysis will be session, however in primary analyses, to avoid an overly complicated model, session will not be modeled as a fixed effect in the regression model for the mean. Fixed effects will include time (baseline and post MP assessment for MP1, 2, or 3) and treatment condition (i.e. whether the clinician's agency is under the intervention or control condition).

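### The session-level ORS/SRS model lists a treatment-condition effect that the planned data cannot estimate, uses undefined time labels, and states no clear MBC-use term for Hypothesis 3 on these two outcomes

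*Combined protocol and SAP*

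**What the plan says.** Section 5.3.1 (Statistical Design) plans a mixed model for ORS and SRS with the session as unit of analysis, allowing for correlation within student and clustering by clinician. Its mean structure is described as: "Fixed effects will include time (baseline and post MP assessment for MP1, 2, or 3) and treatment condition". Condition is explained as the clinician's agency being under intervention or control.

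On allocation, the Synopsis (Study Design) and Section 4.1.1 say: "All clinicians will receive the same implementation supports; there is no random assignment to condition". The Synopsis adds: "There are no group assignments". The only control state is a pre-support period of at least one month, for which Section 4.1.1 schedules clinician data: "During the initial control period, baseline MBC use, attitudes, acceptability, feasibility and appropriateness (per clinician self-report) will be collected", together with a needs assessment. For student data the same section says: "Baseline engagement and student outcomes will be collected after initial clinician training session". ORS and SRS are held in BON, and the Synopsis (Primary Outcome Variables) says: "The MBC training provided as part of this study will include how to use MBC and document it in BON".

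Hypothesis 3 (Section 3.1) reads: "MBC fidelity and use will be positively associated with engagement and mental health symptom and functioning progress over time". Section 4.2.2 assigns student engagement to the SRS, and symptoms and functioning to the ORS. MBC use is named as a predictor in the three-level models, of which Section 5.3.1 says: "Models will be estimated for each parent-reported outcome".

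**The concern.** The session model carries a term for a contrast that the study does not contain. An analyst who fits it as listed will see the term dropped or the fit fail. A worse outcome is that a before-after change gets relabelled as a condition effect. Section 5.3.1 sends the effects and contrasts from all of these analyses to the power calculation for the larger trial, so a mislabelled contrast could be carried forward.

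The time labels also cannot be applied to session records without a mapping that the text does not give. And the term that Hypothesis 3 needs, the relation of MBC use to SRS and ORS, is not among the listed effects. Left as it is, that part of the secondary objective would rest on a model chosen after the data are seen.

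**Working it through.** The plan gives no figure to reproduce here. The question is whether the listed effects can be estimated.

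**Inputs.** Condition, time labels and clustering come from Section 5.3.1. Allocation and timing come from the Synopsis and Section 4.1.1. Assumption: MP1 to MP3 are three periods after baseline, giving four periods.

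**Model.** E(Y) = b0 + b1·T1 + b2·T2 + b3·T3 + g·C, where T1 to T3 indicate the post-baseline periods and C is condition. That is 5 columns.

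**Step 1: as planned.** All sessions follow training, so C = 1 throughout. The distinct rows (intercept, T1, T2, T3, C) are:
- baseline: 1, 0, 0, 0, 1
- MP1: 1, 1, 0, 0, 1
- MP2: 1, 0, 1, 0, 1
- MP3: 1, 0, 0, 1, 1

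C equals the intercept column, so the rank is 4 of 5. Only b0 + g is identified. The contrasts b1, b2 and b3 are estimable; g is not. With one baseline/post indicator in place of T1 to T3, the rank is 2 of 3.

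**Step 2: suppose baseline sessions fell in the control period, with a common start.** Then C = 0 at baseline and 1 afterwards, so C = T1 + T2 + T3. The rank is again 4 of 5, and none of b1, b2, b3 and g is separately estimable. With one baseline/post indicator the rank is 2 of 3.

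**Step 3: what would make condition estimable.**
- Linear time with control-period sessions: rows (1,0,0), (1,1,1), (1,2,1), (1,3,1), rank 3 of 3. Without control-period sessions the rank is 2 of 3.
- Staggered district starts with control-period sessions: rank 5 of 5. Staggered starts with sessions only after each district's own training: rank 4 of 5.

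Both routes need ORS/SRS sessions recorded before supports begin, and the text plans none. It gives no staggered start dates either. The 2021-22 and 2022-23 cohorts do not help, because sessions in each follow training.

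**Step 4: time labels.** *MP* is not in the abbreviation list or glossary and appears nowhere else in the supplied text, from which one part was removed. The follow-up schedule elsewhere is baseline, 3, 6 and 9 months; Table 1 appears to code BON records monthly.

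**Step 5: Hypothesis 3 by outcome.**
- Parent engagement (Therapeutic Alliance Scales): MBC use stated as predictor.
- Symptoms on the PSC-35: MBC use stated as predictor.
- Student engagement (SRS): listed effects are time and condition only.
- Functioning (ORS): listed effects are time and condition only.

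**Step 6: does a replacement work?** Intercept, three time contrasts, clinician-level use and use by linear time give rank 6 of 6. If the last period holds no sessions, the rank falls to 5 of 6. These ranks show that the terms can be identified. They say nothing about precision, since the documents give no variances.

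**The case against.** The strongest defence is the design label. The study is called a clustered multiple-baseline design, with a control period and districts compared with one another and with their own baseline. Condition could then be a term that switches on when supports start. This has force: a reader might infer that condition could not be estimated on any reading, and that goes too far. Linear time, or staggered starts, would identify it if ORS/SRS sessions existed in the control period. What defeats the term is that no such sessions are planned.

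Second, the practical harm is small. With condition constant, dropping it leaves the fit, time contrasts, variances and intra-clinician correlation as they were. That stands. A reader who infers that the session model is worthless, or that the primary analyses are compromised, would not find support in the documents.

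Third, a list of what the fixed effects will include need not be complete, and the three-level paragraph mentions student as well as parent reports. So it cannot be said that MBC use is excluded from the ORS/SRS model, nor that Hypothesis 3 has no test. It has one for parent engagement and the PSC-35. The gap is that the sentence introducing the covariate ties it to parent-reported outcomes, and nothing equally clear is written for SRS or ORS.

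Fourth, the plan wants this model kept simple, and a remedy should respect that. The choice of use measure and the form of its interaction with time are judgements, not corrections.

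**Conclusion.** The point holds, at the level of something that should be fixed in a secondary analysis. On the documented schedule no planned ORS/SRS session falls under a control condition, so the condition effect cannot be estimated (rank 4 of 5) and no sample size cures that. The MP labels match no time point in the supplied text. MBC use has no clearly stated term for SRS or ORS.

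The rank figures assume that MP1 to MP3 are three post-baseline periods; a single baseline/post indicator leads to the same conclusion. The finding that condition is constant rests on Section 4.1.1 placing student outcomes after training. What the model can deliver as listed is uncontrolled change from a post-training baseline, plus variance and clustering estimates for planning. The pilot describes itself as underpowered, which limits the consequence but does not supply the missing contrast.

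**What to change.** Rewrite the ORS/SRS paragraph of Section 5.3.1 as follows.

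- Delete the condition term.
- Replace the MP labels with periods assigned by session date, with explicit windows, or with time since the student's first BON session.
- Add clinician-level MBC use and its interaction with time as the Hypothesis 3 terms for SRS and ORS, keeping student and clinician clustering. CAPER is one suitable measure, already collected pre-training and at 3, 6 and 9 months. A single interaction with linear time keeps the model small.
- State which CAPER survey is linked to each session window, and add a sensitivity analysis leaving out sessions whose linked CAPER is pre-training.
- If use varies over time, separate each clinician's mean from within-clinician change, or use one summary per clinician.
- Collapse the last period if few sessions fall in it. Training in fall 2022 plus nine months reaches about June 2023 or later, and Section 6.12 ends data collection on June 30, 2023.
- Report the use association as exploratory and the time contrasts as uncontrolled change from a post-training baseline. If chart-review fidelity is also used as a predictor, note that Section 5.1.1 defines it by the presence of the same ORS/SRS records.

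The cost is a slightly larger model and a join of CAPER to BON sessions by clinician. Some sessions will have no earlier CAPER, because Section 5.2.2 allows a follow-up survey to be a clinician's first; report how many. The control contrast given up was never available.

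As a separate point, reconcile the wording on aggregate versus linked BON data, both within Section 5.1.1 and between it and Section 5.2.

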5.3.2 Sample Size Considerations

We plan to enroll 50 SMH clinicians and up to 150 parents of children or adolescents with mental illness. The rationale for this sample size is based on having a large enough sample of clinicians trained that a range of implementation outcomes can be observed and described as pilot data for a larger-scale, fully-powered study. The rationale for the 150 students is based on our prior research in quality improvement and implementation research in schools, where it is more feasible to introduce a new practice to clinicians by telling them they can select a subset of their caseload for MBC implementation. We will outreach to students the clinician reports they are using MBC with. Selection of a subset of cases will involve a random selection of recently consented cases.

5.3.3 Planned Analyses

Please see details in 5.4.1

5.3.4 Analysis of Subject Characteristics (if applicable)

Quality control checks of the data and examination of variable distributions will be performed prior to formal analysis. Descriptive statistics and intercorrelations will be examined for all datasets. Demographic characteristics of clinician participants and parent/guardian participants will be examined and reported in all scholarly reports and products. If any demographic characteristics are significantly related to implementation or effectiveness outcomes, they will be entered as control variables in the linear mixed analyses.

5.3.5 Interim Analysis (if applicable)

Not applicable.

5.3.6 Handling of Missing Data

Missing data will be analyzed to examine any patterns of missingness not at random, including case-wise (i.e., overall percentage, patterns, various longitudinal intervals of missingness) and variable-wise (i.e., overall percentage, patterns) missing values analysis. Linear mixed modeling is robust to missing data and does not require listwise deletion of cases with missing data. Therefore, if missing data are missing at random (MAR) all data will be used. Otherwise, analyses with and without missing data will be compared to examine whether results differ when including cases and variables with data missing not at random.

6 Trial Administration

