5.2.2 Recruitment, Enrollment and Retention (if applicable)

5.3.3 Clinician Participants

Clinicians (N=50) who provide psychosocial interventions to K-12 students in our identified districts will be informed of the project using the following steps:

1. Clinicians receive an email from their supervisor (e.g., a “site leader” which could be a district or community mental health agency administrator, depending on whether

they are school- or community-employed) that the FOCUSS study team will contact them directly about participation. See “Clinician Notice of FOCUSS Study Email from Site Leader”. This will include “FOCUSS Flyer – Clinician”.

2. Site leaders will send the study team a list of names and email addresses of eligible clinicians.
3. Study team members will email clinicians directly with the “FOCUSS Flyer – Clinician” form attached. The email message will remind clinicians about the project and include a link to the first online survey. See “Qualtrics Invitation Email from Study Team – Clinicians”
4. Clinicians can view the Clinician Information Sheet and FOCUSS Flyer-Clinician on the first page of the online Qualtrics survey and provide contact information for the study team for any questions or clarifications they may have.
5. Two (2) reminders will be sent to clinicians who do not open the survey link. All clinicians will receive emails about the 3 month, 6 month, and 9 month surveys regardless of baseline survey completion. All follow-up surveys will include a link to the Clinician Information Sheet and FOCUSS Flyer-Clinician on the first page, as a reminder, and for any clinicians completing a follow-up survey as their first survey.

Parent/Guardian Participants

Consent will be collected over the phone for parents. Parent/guardians (N=150) who have a child receiving school-based mental health treatment from one of the participating clinicians will be recruited and consented using the following steps:

1. The clinician and/or designated site clinical staff will ask the parent/guardian of each recruited student if they are willing to be contacted by the study team. They will do this using the “Clinician Parent/Guardian Recruitment Script”.
2. If so, the parent’s contact information will be shared with relevant study team member using the “Research Interest Sheet – FOCUSS”, who will contact the parent via phone and/or email and then introduce the study, read the consent form, and request informed consent over the phone.

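### The claim in 5.3.6 that all data will be used holds for missing outcomes, but the parent-outcome models take clinician-survey covariates and no method is named for when those are missing

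*Combined protocol and SAP*

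**What the plan says.** Section 5.3.6 (Handling of Missing Data) makes two linked statements. The first is that "Linear mixed modeling is robust to missing data and does not require listwise deletion of cases with missing data". The second draws the consequence: "Therefore, if missing data are missing at random (MAR) all data will be used". The section also plans to describe missingness by case and by variable. If data are not MAR, it plans to compare results with and without the affected cases and variables. It names no imputation or joint modelling.

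Section 5.3.1 (Statistical Design) sets out the models. For the parent-reported outcomes (engagement and PSC-35) it plans a 3-level growth model and says: "Independent variables that will be entered as covariates in these models include MBC implementation outcomes". The stated expectation is that MBC use predicts better engagement and fewer symptoms. For the clinician outcomes, attitudes toward MBC are entered together with "clinician professional and demographic characteristics, consultation call attendance, school district". Section 5.3.4 adds demographics that prove significant: "they will be entered as control variables in the linear mixed analyses". The ORS/SRS session model is different: "Fixed effects will include time (baseline and post MP assessment for MP1, 2, or 3) and treatment condition".

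Table 1 in 5.1.1 shows that AIM, IAM, FIM and self-reported use (CAPER) come only from the clinician online survey, before training and at 3, 6 and 9 months. Fidelity is coded by the study team from chart review or BON. The clinician recruitment steps foresee skipped surveys: "All clinicians will receive emails about the 3 month, 6 month, and 9 month surveys regardless of baseline survey completion". The survey's first page is also written "for any clinicians completing a follow-up survey as their first survey".

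**The concern.** A likelihood-based mixed model uses an incomplete series of outcomes without discarding the subject, and under MAR that is valid. But it conditions on the predictors. A row with an observed outcome and a missing predictor contributes nothing unless the predictor is imputed or given its own model. The plan does neither, so the second statement in 5.3.6 goes further than the method allows.

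The gap matters most in the parent-outcome models, because outcome and predictor come from different people. The parent answers by telephone and the clinician answers online, so a clinician's silence can remove data that the parent supplied.

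Two things are at stake. Parent interviews already collected would go unused while the plan says that all data were used. The association between self-reported use and family outcomes would also be estimated only on waves in which the clinician responded. That estimate is biased if clinician non-response is related to family outcomes given the predictors. Section 5.3.1 intends these estimates, with the intra-clinician correlation and variance, to inform the power analysis for a larger trial.

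**Working it through.** The documents state no response rate, dropout rate or expected row count, so there is no plan figure to reproduce. The check has three parts.

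**1. Which models are exposed**

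| Model (5.3.1) | Clinician-survey predictor? | Observed rows lost when a whole survey is skipped |
|---|---|---|
| Growth model with time only | No | None |
| Clinician growth model with attitudes | Yes, from the same survey as the self-reported outcome | Almost none extra: outcome and predictor go missing together |
| ORS/SRS session model | No (time and condition only) | None |
| Parent-outcome model, BON-coded fidelity only | No | None |
| Parent-outcome model, self-reported use, AIM, IAM or FIM | Yes, from a different reporter | Yes, if wave-matched |

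**2. Row counts for the exposed model**

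Inputs from the documents: 50 clinicians and up to 150 parents (5.3.2), and four parent interviews (5.2).

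- Families per clinician: 150 / 50 = 3.
- Maximum parent rows: 150 x 4 = 600.

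Assumptions, none of them in the documents:

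- Parent completion is 100/90/80/75% over the four waves.
- Clinician response is as in the table below.
- The two are independent.
- The survey covariate is time-varying and matched to the parent wave.

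Observed parent rows = 150 x (1.00 + 0.90 + 0.80 + 0.75) = 150 x 3.45 = 517.5.

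Rows kept = 150 x sum over waves of (parent completion x clinician response).

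| Clinician response by wave | Sum of products | Rows kept | Rows lost |
|---|---|---|---|
| 90/85/80/75% | 0.900 + 0.765 + 0.640 + 0.5625 = 2.8675 | 430.1 | 87.4 (17%) |
| 85/75/65/60% | 0.850 + 0.675 + 0.520 + 0.450 = 2.495 | 374.3 | 143.3 (28%) |
| 80/70/60/50% | 0.800 + 0.630 + 0.480 + 0.375 = 2.285 | 342.8 | 174.8 (34%) |

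A simpler version assumes flat clinician non-response of 10/20/30/40%. With every parent call complete, 60/120/180/240 of 600 rows are lost. With 20% of calls missed (480 observed), 48/96/144/192 are lost. The proportion lost is the clinician non-response rate itself.

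**3. Simulation of the same layout**

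Data were simulated for 50 clinicians, three families each and four waves, with every parent outcome present. Clinician surveys were made missing with a probability that depended on the observed mean outcome of that clinician's families at that wave, so the missingness was MAR.

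- In one data set, 18.5% of rows lacked the survey predictor. The mixed model with that predictor kept 489 of 600 rows, and the time-only model kept all 600.
- Over 200 data sets, with about 21% of rows lacking the predictor, the predictor slope averaged 0.287 on retained rows against 0.306 on full data (true value 0.30; Monte Carlo standard errors 0.004 and 0.003). The time slope averaged 0.186 against 0.197 (true value 0.20).

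The fitted models had a random clinician intercept only, and some fits gave convergence warnings. The slopes therefore show direction and rough size, not a precise bias.

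**The case against.** The strongest reply has five parts.

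- **Cases and rows differ.** Section 5.3.6 speaks of deleting cases. A family lacking the predictor at one wave stays in the model through its other waves. This stands: the first sentence is defensible for wave-level gaps, and it is the second, on using all data, that is too strong.
- **Predictor missingness is not ignored.** The variable-wise analysis would show it. This stands too, but describing a gap does not handle it. The comparison planned for data not MAR cannot bring back rows that the model has no means of using.
- **Hypothesis 3 does not rest on the survey alone.** Section 3.1 states it for fidelity, from review of the feedback system, and for self-reported use. A reader might infer that all of Hypothesis 3 would be estimated only on families of clinicians who answer surveys. The documents do not support that, because a model using BON-coded fidelity loses nothing to a skipped survey.
- **The covariates may not be wave-matched.** Section 5.3.1 does not say how they enter. If each clinician's measures are summarised at Level 3, one missed survey need lose no parent rows. This stands as a condition on the size of the loss.
- **Non-response may be low.** Section 5.1 offers a gift card per survey, and the recruitment steps include two reminders. No rate is given either way.

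A reader might also infer that clinicians who skip the first survey, with their families, leave every adjusted model because their characteristics are asked only once. Section 6.6 lists a Welcome Survey and a Follow-Up Survey, but the contents of the forms are not in the documents, so this cannot be claimed.

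**Conclusion.** The point holds for the parent-outcome models with clinician-survey covariates, which belong to a secondary objective of a pilot that section 3.1 itself describes as underpowered. There the statement that all data will be used is wrong as written, and no method is given for a missing survey predictor. The loss is about 17% to 34% of observed parent rows. That range rests on assumed response rates, on independence of parent and clinician response, and on wave-matched covariates. It shrinks if clinician-level summaries are used.

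Two stronger readings should be avoided. One is that the primary analyses are compromised. Time-only growth models have no survey predictor, and a wholly skipped survey costs the clinician models almost nothing beyond the outcome already missing. Item non-response, or demographics brought in under 5.3.4, could add some loss. The other is that Hypothesis 3 would be seriously biased. Bias is possible, but it was small in the one simulation run. The firmer consequences are unused parent data and an inaccurate statement about which data were used. The change is worth making before analysis because it is cheap.

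**What to change.** 1. In 5.3.6, limit the statements on listwise deletion and on using all data to missing outcomes.
2. In 5.3.1, state whether survey covariates enter the parent-outcome models by wave or as clinician-level summaries.
3. For those models, name a method for missing survey predictors: multilevel multiple imputation that includes the parent outcome and BON-coded use, or joint modelling of predictor and outcome.
4. Report the BON-fidelity model, already within the plan, alongside as the version that does not depend on survey response. Define its value for the period before training, and say how a clinician with no BON entries is treated, since that may mean non-use or non-recording.
5. For every model, report rows and clinicians available and used.

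The cost is revised wording, submitted to the IRB as section 6.11 requires, and moderate extra programming. No new data are needed. The main limitation is that the imputation model must stay simple with 50 clinicians and about three families each.
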